7.3.1.1.3 Immune-mediated adverse reactions

Immune-mediated adverse reactions occurred in patients receiving pembrolizumab. In clinical trials, most immune-mediated adverse reactions were reversible and managed with interruptions of pembrolizumab, administration of corticosteroids and/or supportive care.

For suspected immune-mediated adverse reactions, ensure adequate evaluation to confirm etiology or exclude other causes. Based on the severity of the adverse reaction, withhold pembrolizumab and administer corticosteroids (see below). Upon improvement to Grade 1 or less, initiate corticosteroid taper and continue to taper over at least 1 month. Restart pembrolizumab if the adverse reaction remains at Grade 1 or less. If another episode of a severe adverse reaction occurs, permanently discontinue pembrolizumab.

Immune-mediated pneumonitis

Pneumonitis has been reported in patients receiving pembrolizumab. Monitor patients for signs and symptoms of pneumonitis. If pneumonitis is suspected, evaluate with radiographic imaging. Exclude other causes of pneumonitis, and manage treatment in accordance with the guidelines above. Administer corticosteroids, withhold pembrolizumab for moderate (Grade 2) pneumonitis, and permanently discontinue pembrolizumab for severe (Grade 3) or life-threatening (Grade 4) pneumonitis (see Immune-mediated adverse reactions above). If Grade 2 pneumonitis is repeated pembrolizumab will be discontinued permanently.

Immune-mediated colitis

Colitis has been reported in patients receiving PEMBROLIZUMAB. Monitor patients for signs and symptoms of colitis. Exclude other causes of colitis, and manage treatment in accordance with the guidelines above. Administer corticosteroids, withhold pembrolizumab for moderate (Grade 2) or severe (Grade 3) colitis, and permanently discontinue pembrolizumab for life-threatening (Grade 4) colitis (see Immune-mediated adverse reactions above).

Immune-mediated hepatitis

Hepatitis has been reported in patients receiving pembrolizumab. Monitor patients for changes in liver function (at the start of treatment, periodically during treatment and as indicated based on clinical evaluation) and symptoms of hepatitis. Exclude other causes of hepatitis, and manage treatment in accordance with the guidelines above. Administer corticosteroids and, based on severity of liver enzyme elevations, withhold or discontinue pembrolizumab (see Immune-mediated adverse reactions above).

Immune-mediated nephritis

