Across clinical studies with pembrolizumab in approximately 5000 patients, the following additional clinically significant, immune-mediated adverse reactions were reported in less than 1% of patients: uveitis and severe skin reactions.

Infusion-related reactions

Across clinical studies with pembrolizumab in approximately 5000 patients, severe infusion-related reactions have been reported in less than 0.1% of patients. For severe infusion reactions, stop infusion and permanently discontinue pembrolizumab. Patients with mild or moderate infusion reaction may continue to receive pembrolizumab with close monitoring; premedication with antipyretic and antihistamine may be considered.

General Approach to Handling irAEs

irAE grade	Withhold/discontinue	Supportive care
Grade 1	No action	Provide symptomatic treatment
Grade 2	May withhold pembrolizumab	Consider systemic corticosteroids in

(With repeated hepatitis and pneumonitis, pembrolizumab should be stopped)		addition to appropriate symptomatic treatment
Grade 3 and 4	Withhold pembrolizumab Discontinue if unable to reduce corticosteroid dose to <10 mg per day prednisone equivalent within 12 weeks of toxicity	Systemic corticosteroids are indicated in addition to appropriate symptomatic treatment. May utilize 1-2 mg/kg prednisone or equivalent per day. Steroid taper should be considered once symptoms improve to Grade 1 or less and tapered over at least 4 weeks.

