15.2 Toxicity management guidelines for immune-related AEs associated with pembrolizumab

General instructions:				

 1. Corticosteroid taper should be initiated upon AE improving to Grade 1 or less and continue to taper over at least 4 weeks. 2. For situations where pembrolizumab has been withheld, pembrolizumab can be resumed after AE has been reduced to Grade 1 or 0 and corticosteroid has been tapered. Pembrolizumab should be permanently discontinued if AE does not resolve within 12 weeks of last dose or corticosteroids cannot be reduced to ≤ 10 mg prednisone or equivalent per day within 12 weeks. 3. For severe and life-threatening irAEs, IV corticosteroid should be initiated first followed by oral steroid. Other immunosuppressive treatment should be initiated if irAEs cannot be controlled by corticosteroids. 				
Pneumonitis	Grade 2	Withhold	
 Administer corticosteroids (initial dose of 1-2 mg/kg prednisone or equivalent) followed by taper 	
 Monitor participants for signs and symptoms of pneumonitis Evaluate participants with suspected pneumonitis with radiographic imaging and initiate corticosteroid treatment Add prophylactic antibiotics for opportunistic infections
	Grade 3 or 4, or recurrent Grade 2	Permanently discontinue		
Diarrhea / Colitis	Grade 2 or 3	Withhold	
 Administer corticosteroids (initial dose of 1-2 mg/kg prednisone or equivalent) followed by taper 	
 Monitor participants for signs and symptoms of enterocolitis (ie, diarrhea, abdominal pain, blood or mucus in stool with or without fever) and of bowel perforation (ie, peritoneal signs and ileus). Participants with \geq Grade 2 diarrhea suspecting colitis should consider GI consultation and performing endoscopy to rule out colitis. Participants with diarrhea/colitis should be advised to drink liberal quantities of clear fluids. If sufficient oral fluid intake is not feasible, fluid and electrolytes should be substituted via IV infusion.
	Grade 4	Permanently discontinue		

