All other immune-related AEs	Intolerable/persistent Grade 2	Withhold	
Based on type and severity of AE administer corticosteroids	
Ensure adequate evaluation to confirm etiology and/or exclude other causes
	Grade 3	Withhold or discontinue based on the type of event. Events that require discontinuation include and not limited to: Guillain-Barre Syndrome, encephalitis		
	Grade 4 or recurrent Grade 3	Permanently discontinue		

1. Withhold or permanently discontinue pembrolizumab is at the discretion of the investigator or treating physician.

NOTE:

For participants with Grade 3 or 4 immune-related endocrinopathy where withhold of pembrolizumab is required, pembrolizumab may be resumed when AE resolves to ≤ Grade 2 and is controlled with hormonal replacement therapy or achieved metabolic control (in case of T1DM). ⁱ

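### The general immune-event table in section 7.3.1.1.3 permits pembrolizumab where Appendix 15.2 requires a hold or a permanent stop, for first Grade 4 events without their own paragraph and for myocarditis

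*Combined protocol and SAP*

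**What the plan says.** Two parts of the protocol tell the investigator what to do with pembrolizumab after an immune-related event.

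**Section 7.3.1.1.3.** The opening paragraph gives a general restart rule: "Restart pembrolizumab if the adverse reaction remains at Grade 1 or less". Its general stopping rule is "If another episode of a severe adverse reaction occurs, permanently discontinue pembrolizumab". Paragraphs on individual organs follow. The section closes with a table, General Approach to Handling irAEs, organised by grade alone. Grade 1 needs no change to the drug. Grade 2 reads "May withhold pembrolizumab", with a stop for repeated hepatitis and pneumonitis. Grades 3 and 4 share one row: withhold, then "Discontinue if unable to reduce corticosteroid dose to <10 mg per day prednisone equivalent within 12 weeks of toxicity".

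**Appendix 15.2.** Its rows are organised by event and grade. The last row, for all other immune-related events, orders permanent discontinuation for "Grade 4 or recurrent Grade 3". At Grade 3 the choice depends on the event: "Events that require discontinuation include and not limited to: Guillain-Barre Syndrome, encephalitis". Myocarditis has its own row: withhold at Grade 1 or 2, stop permanently at Grade 3 or 4. General instruction 2 adds time limits: "Pembrolizumab should be permanently discontinued if AE does not resolve within 12 weeks of last dose or corticosteroids cannot be reduced" to 10 mg/day of prednisone or less within 12 weeks.

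The end of the hepatic guidance in section 6.3.1 (after Table 6.6) sends the reader to a section 16.2 for pembrolizumab toxicity guidelines. There is no section 16.2; the guidelines are in 15.2.

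**The concern.** Giving a checkpoint inhibitor again after a life-threatening immune event, or continuing it through early myocarditis, is a patient-safety decision. For some events both instructions apply to the same patient on the same day and cannot both be followed. Section 13.1 demands strict adherence to the protocol, and section 3 foresees one or two further institutions, so two sites could each follow the text and act differently.

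**Working it through.** This is a comparison of texts; the plan has no figure to reproduce.

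**Step 1. Where the instructions collide.** All rows are first occurrences.

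| Event | Section 7.3.1.1.3 (general table and restart sentence) | Appendix 15.2 |
|---|---|---|
| Grade 4 event with no paragraph of its own, e.g. uveitis | Withhold; restart possible at Grade 1 or lower | Permanent stop |
| Guillain-Barre syndrome or encephalitis, Grade 3 | Withhold; restart possible at Grade 1 or lower | Discontinue |
| Myocarditis, Grade 1 | No action | Withhold |
| Myocarditis, Grade 2 | Optional hold | Withhold |
| Myocarditis, Grade 3 or 4 | Withhold; restart possible at Grade 1 or lower | Permanent stop |

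For the events that the body text only withholds, the difference matters when the patient recovers and steroids come down in time. If the taper fails, both texts stop the drug.

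Uveitis is the cleanest example. Section 7.3.1.1.3 names it but gives no action, so the grade table applies. In the appendix it falls in the all-other row. Both are residual rules, so reading the specific over the general does not settle the case.

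**Step 2. Where they do not collide.** The organ paragraphs agree with the appendix on holding and stopping by grade for pneumonitis, colitis, nephritis and hypophysitis. Both texts stop on a recurrent severe event.

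**Step 3. Time limits.** The appendix resolution limit is 12 × 7 = 84 days from the last dose. Suppose a held Grade 2 event, treated without systemic steroids, reaches Grade 1 on day 90. That is 90 − 84 = 6 days late, and the appendix stops the drug. The restart sentence has no deadline, and the Grade 2 row has none. This is silence in one place that the other place fills: applying the appendix limit breaks nothing in section 7.3.1.1.3.

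The general limit is the only one for at least 4 of the 10 appendix rows: pneumonitis, nephritis, myocarditis, and all other events apart from rash. The other 6 (diarrhea/colitis, liver tests, four endocrine rows) have a limit or restart rule elsewhere, although the endocrine note covers only Grades 3 and 4.

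The steroid limit cannot carry a worked case, because general instruction 2 does not say when its 12 weeks begin. For toxicity on day 14 after the last dose and steroids from day 21 (assumed dates), the limit could be day 84 (last dose), 14 + 84 = day 98 (onset), or 21 + 84 = day 105 (start of steroids). A patient on 15 mg/day on day 98 fails the first two but might pass the third.

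**Step 4. Size.** Section 7.3.1.1.3 describes additional reactions "reported in less than 1% of patients: uveitis and severe skin reactions". Section 10.1 caps the trial at 75 patients. If that pembrolizumab rate applies to the combination, 0.01 × 75 = 0.75, so fewer than 0.75 patients per event type. This bound covers all grades; Grade 4 events would be fewer. The documents give no rate for myocarditis or for immune events on the combination.

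**The case against.** The strongest reply is that the protocol already sends investigators to the appendix. The pointer after Table 6.6 is misnumbered, but its wording matches the title of Appendix 15.2 and the target is clear. The table in section 7.3.1.1.3 is labelled a general approach, so the myocarditis row should win as the more specific rule. Section 5.2.1 also requires withdrawal when the investigator judges continuation harmful.

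Part of this stands. A reader might infer that nothing leads from the body of the protocol to the appendix; the pointer shows otherwise. But it sits at the end of hepatic guidance, does not mention section 7.3.1.1.3 and sets no order of precedence. Nothing in section 7.3.1.1.3 refers to Appendix 15.2, so a reader who looks up myocarditis there finds only the grade table. Specific-over-general reading does not help uveitis.

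A reader might also infer that the 12-week limits contradict each other. The documents support less: the appendix supplies limits that the body mostly omits. The remaining difference, below 10 mg/day in the table against 10 mg/day or less in the appendix, affects only a patient at exactly 10 mg/day, and the symbol could be an artefact of text extraction.

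**Conclusion.** The conflict is real on the two actions in Step 1. For a first Grade 4 immune event with no paragraph of its own, and for myocarditis, section 7.3.1.1.3 allows dosing or re-dosing that Appendix 15.2 forbids. The missing time limits are a gap, not a contradiction. Reach is narrow: fewer than 0.75 patients for uveitis if the quoted rate carries over, and unknown for myocarditis.

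Two stronger conclusions should be resisted. One is that the appendix should override all of section 7.3.1.1.3. The body text is stricter in places: it makes the stop for Grade 4 hyperthyroidism mandatory where the appendix leaves it to discretion, and it stops for repeated Grade 2 hepatitis where the appendix has no recurrence rule. The other is that the primary analysis is affected; nothing in the documents supports an effect on PFS or sample size.

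The conclusion assumes only that the grade table and restart sentence are read as written for events that section 7.3.1.1.3 does not treat separately.

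**What to change.** 1. In the general table, replace the Grade 3 and 4 action with that of the appendix's all-other row: permanent stop for Grade 4 or recurrent Grade 3; withhold or discontinue by event type at Grade 3. Refer to the appendix row for myocarditis of any grade.
2. Cross-refer the restart sentence and the table to general instruction 2 for any event for which the drug is held, including Grade 2. Say when its 12-week steroid limit starts; this is a new choice.
3. Correct 16.2 to 15.2 in the pointer after Table 6.6.
4. State that Appendix 15.2 replaces the general table and the general restart rule, and that event-specific rules take precedence over general ones. Keep the permanent stop for Grade 4 hyperthyroidism and the stop for repeated Grade 2 hepatitis unless the sponsor expressly changes them.
5. Have the sponsor settle three event-specific pairs that still differ:
   - Grade 3 or 4 hepatitis: Tables 6.5 and 6.6 allow restart after ALT/AST above 5 × ULN; the appendix stops permanently.
   - Grade 2 diarrhea: Table 6.7 holds only if it persists beyond 7 days; the appendix withholds.
   - Recurrent Grade 3 diarrhea: Table 6.7 stops permanently; the appendix row is silent on recurrence.

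The cost is protocol wording, with no extra data, visits or patients.

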7.3.1.1.4 Causal relationship

The assessment of the causal relationship between an AE and the administration of treatment is a clinical decision based on all available information.

The causality assessment should be done separately for each study treatment.

The assessment is based on the question whether there was a “reasonable causal relationship” to the study treatment in question.

Possible answers are “yes” or “no”.

An assessment of “no” would include:

1. The existence of a clear alternative explanation, e.g. mechanical bleeding at surgical site.

or

2. Non-plausibility, e.g. the subject is struck by an automobile when there is no indication that the drug caused disorientation that may have caused the event; cancer developing a few days after the first drug administration.

An assessment of “yes” indicates that there is a reasonable suspicion that the AE is associated with the use of the study treatment.

Factors to be considered in assessing the relationship of the AE to study treatment include:

- The temporal sequence from drug administration: The event should occur after the drug is given. The length of time from drug exposure to event should be evaluated in the clinical context of the event.
- Recovery on drug discontinuation (de-challenge), recurrence on drug re-introduction (re-challenge):

- Subject's response after de-challenge or subject's response after re-challenge should be considered in the view of the usual clinical course of the event in question.
- Underlying, concomitant, intercurrent diseases:
Each event should be evaluated in the context of the natural history and course of the disease being treated and any other disease the subject may have.
- Concomitant medication or treatment:
The other drugs the subject is taking or the treatment the subject receives should be examined to determine whether any of them may be suspected to cause the event in question.
- The pharmacology and pharmacokinetics of the study treatment:
The pharmacokinetic properties (absorption, distribution, metabolism and excretion) of the study treatment, coupled with the individual subject's pharmacodynamics should be considered.

[Causal relationship to protocol-required procedure(s)]

The assessment of a possible causal relationship between the AE and protocol-required procedure(s) is based on the question whether there was a "reasonable causal relationship" to protocol-required procedure(s).

Possible answers are "yes" or "no".

7.3.1.1.5 Action taken with study treatment

Any action on study treatment to resolve the AE is to be documented using the categories listed below.

The study treatment action should be recorded separately for each study treatment.

- Drug withdrawn
- Drug interrupted
- Dose reduced
- Dose not changed
- Dose increased
- Not applicable
- Unknown

7.3.1.1.6 Other specific treatment(s) of adverse events

- None
- Remedial drug therapy

7.3.1.1.7 Outcome

The outcome of the AE is to be documented as follows:

- Recovered/resolved
- Recovering/resolving
- Recovered/resolved with sequelae
- Not recovered/not resolved
- Fatal
- Unknown

Assessments and documentation of adverse events

The definition of adverse events (AEs) is given on Section 7.3.1.1.

All AEs, SAEs and other reportable safety events that occur after the consent form is signed but before treatment allocation/randomization must be reported by the investigator.

- All AEs from the time of treatment allocation/randomization through 30 days following cessation of study treatment must be reported by the investigator.
- All AEs meeting serious criteria, from the time of treatment allocation/randomization through 30 days following cessation of study treatment if the participant initiates new anticancer therapy, whichever is earlier must be reported by the investigator.
- All pregnancies and exposure during breastfeeding, from the time of treatment allocation/randomization through 120 days following cessation of study treatment, or 30 days following cessation of study treatment if the participant initiates new anticancer therapy must be reported by the investigator.
- Additionally, any SAE brought to the attention of an investigator at any time outside of the time period specified above must be reported immediately by the investigator if the event is considered to be drug-related.

Investigators are not obligated to actively seek AE or SAE or other reportable safety events in former study participants. However, if the investigator learns of any SAE, including a death, at any time after a participant has been discharged from the study, and he/she considers the event to be reasonably related to the study treatment or study participation, the investigator must promptly notify Merck.

Reporting of serious adverse events

The definition of serious adverse events (SAEs) is given on Page Section 7.3.1.2.

Each serious adverse event must be followed up until resolution or stabilization, by submission of updated reports to the designated person. An isolated laboratory abnormality that is assigned grade 4, according to CTC definition, is not reportable as an SAE; unless the investigator assesses that the event meets standard ICH criteria for an SAE. CTC grade 4 baseline laboratory abnormalities that are part of the disease profile should not be reported as an SAE, specifically when they are allowed or not excluded by the protocol inclusion/exclusion criteria.

Throughout the course of the STUDY, the Principal Investigator and study personnel agree to comply with the obligations of adverse event reporting as set forth below, 'Safety Reporting Requirements' and with FDA regulations.

SPONSOR/ INSTITUTION is responsible for all the pharmacovigilance obligations and safety reporting pursuant to the applicable law and regulations in the country where the STUDY is performed.

Additionally, the SPONSOR/INSTITUTION shall immediately, within 24 hours at the latest, report to BAYER by fax or and/or email and to Merck. Merck Global Safety. (Attn: Worldwide Product Safety; [contact]).

(1) any other relevant safety information including but not limited to:

- a. reports of drug exposure via mother / father with and without adverse events (exposure during conception, pregnancy, childbirth and breastfeeding) including their outcome;
- b. if linked to a serious adverse event, reports of misuse, abuse, overdose , medication error and other uses outside what is foreseen in the protocol, drug dependency, occupational exposure, suspected transmission of an infectious agent, withdrawal syndrome, drug interactions with respect to the STUDY DRUG;

and

(2) any communication concerning safety related information to regulatory authorities or ethics committees including but not limited to:

- Development Safety Update Reports / relevant parts of IND reports for the STUDY;
- Any other safety related reports, issues and queries that are either raised by or communicated to regulatory authorities or ethics committees (e.g. reportable non-serious cases);

CONTRACT PARTNERS commit to promptly respond to any query from BAYER and Merck regarding adverse event documentation. This will include queries related to specific treatment assignment for reported Serious Unexpected Adverse Drug Reactions.

Safety Reporting Requirements

The PRINCIPAL INVESTIGATOR must accept full responsibility for the trial and the safety of the subjects participating in the trial. The PRINCIPAL INVESTIGATOR is responsible for the ongoing safety evaluation of the study and shall provide to USC, BAYER and MERCK all Serious Adverse Events (SAEs) within 24 hours of the PRINCIPAL INVESTIGATOR'S awareness.

Adverse Drug Reaction (ADR):

All noxious and unintended responses to a medicinal product related to any dose should be considered adverse drug reactions. The phrase "responses to a medicinal product" means in view of the investigator and/or company that a causal relationship between a medicinal product and an adverse event is at least a reasonable possibility and that the adverse event is associated with the use of the drug.

Serious Adverse Drug Reaction (SADR):

A Serious Adverse Drug Reaction is an event that meets any of the criteria for seriousness as previously defined and has a possible causal relationship to the study drug.

Requirements for Reporting of Serious Adverse Events:

All SAEs must be reported to USC, Bayer and Merck within 24 hours of the Principal Investigator's awareness and must include the following minimum information:

- 1. The name and contact information of the reporter**
- 2. The name of the study drug(s)**
- 3. A description of the reported SAE**
- 4. A patient identified by one or more of the following:**
 - a. Patient initials**
 - b. Patient number**
 - c. Knowledge that a patient who experienced the adverse event exists**
 - d. Age**
 - e. Sex**
- 5. An investigator assessment of study drug causality. For studies with combination therapy, a separate causality assessment should be provided for each study drug.**

Additional data which would aid the review and causality assessment of the case include but are not limited to:

The date of onset

The severity

The time from administration of study drug(s) to start of the event

The duration and outcome of the event

Any possible etiology for the event

The final diagnosis or syndrome, if known

Action(s) taken, if any

For blinded studies, the Principal Investigator will provide the treatment assignment upon request for patients who experience SAEs. The Principal Investigator will provide the final treatment assignment immediately after the end of the study.

Expedited Reporting of Other Safety Information:

The Investigator/ Sponsor shall report to USC, Bayer and Merck within 24 hours of the investigator's awareness of other events such as:

- An adverse event related to study specific procedures
- Any new and important event related to treatment with the study drug(s).
- Any pregnancy during which a female patient was exposed to the study drug(s)
- Any pregnancy in the partner of a male patient, where the male patient was exposed to study drug at the time of conception or conception occurred within two weeks of the last dose of study drug(s).
- Any other relevant safety information including but not limited to reports on drug interaction, overdose, drug abuse or misuse, drug dependency, withdrawal syndrome, medication error, occupational exposure and lack of drug effect (LODE) occurring at any time during the treatment phase;

Any communication concerning safety related information to regulatory authorities or ethics committees including but not limited to:

- Development Safety Update Reports (DSUR) / relevant parts of IND reports for the STUDY;
- Any other safety related reports, issues and queries that are either raised by or communicated to regulatory authorities or ethics committees;

The Investigator/Sponsor may report SAEs using:

A MedWatch 3500A form available at <http://www.fda.gov/medwatch/>

All reports shall be sent to:

[contact]; [contact] and Merck Global Safety. (Attn: Worldwide Product Safety; [contact]).

Facsimile: Bayer:[contact] and Merck [contact]

Address: Global Pharmacovigilance - USA
Mail only Bayer HealthCare
[name]
[name]

Address: [name]
FDX or UPS only [name] for UPS

Reports for all Bayer products can also be phoned in via our Medical Communications Department

[contact]

The Principal Investigator commits to respond promptly to any query from Bayer regarding SAE reports.

Expected adverse events

For this study, the applicable reference document is the most current version of the investigator's brochure (IB) / summary of product characteristics.

Overview listings of frequent events that have occurred so far in the clinical development are shown in the current IB. If relevant new safety information is identified, the information will be integrated into an update of the IB and distributed to all participating sites.

Adverse events of special safety interest

Bayer: As with any new chemical entity, there is always potential for unexpected adverse events, including hypersensitivity reactions.

Based on data studies with regorafenib and from current knowledge of the pharmacological properties of other small molecule tyrosine kinase inhibitors in this drug class, as soon as there is reasonable suspicion of any of the following AEs, the investigator should immediately notify the sponsor as outlined in Section 7.4.1.4.

Reportable adverse events include:

- Acute renal failure (NCI-CTCAE version 5.0 \geq grade 3) or severe proteinuria (NCI-CTCAE version 5.0 \geq grade 3)
- Interstitial lung disease
- Acute cardiac failure
- Clinically significant bleeding (NCI-CTCAE version 5.0 \geq grade 3)
- Stevens-Johnson Syndrome and erythema multiforme
- Hepatic failure
- Reversible posterior leukoencephalopathy syndrome
- Gastrointestinal perforation or fistula

Merck:

Selected non-serious and serious adverse events are also known as Events of Clinical Interest (ECI) and must be reported within 2 working days to Merck Global Safety. (Attn: Worldwide Product Safety; [contact]).

For the time period beginning when the consent form is signed until treatment allocation, any ECI, or follow up to an ECI, that occurs to any participant must be reported within 2 working days to Merck Global Safety if it causes the participant to be excluded from the trial, or is the

result of a protocol-specified intervention, including but not limited to washout or discontinuation of usual therapy, diet, placebo treatment or a procedure.

For the time period beginning at treatment through 90 days following cessation of treatment, or 30 days following cessation of treatment if the participant initiates new anticancer therapy, whichever is earlier, any ECI, or follow up to an ECI, whether or not related to Merck product, must be reported within 2 working days to Merck Global Safety.

Events of clinical interest for this trial include:

1. an overdose of Merck product that is not associated with clinical symptoms or abnormal laboratory results.
2. an elevated AST or ALT lab value that is greater than or equal to 3X the upper limit of normal and an elevated total bilirubin lab value that is greater than or equal to 2X the upper limit of normal and, at the same time, an alkaline phosphatase lab value that is less than 2X the upper limit of normal, as determined by way of protocol-specified laboratory testing or unscheduled laboratory testing.*

*Note: These criteria are based upon available regulatory guidance documents. The purpose of the criteria is to specify a threshold of abnormal hepatic tests that may require an additional evaluation for an underlying etiology.

